Secondary Endpoints: 1) Improvement in balance and fall risk as measured at baseline and 4 weeks. 2) 48 Hours of continuous daily physical activity using a validated body worn sensor as measured at baseline and 4 weeks. 3) Gait assessment at baseline and 4 weeks.

Specific Aim and Hypothesis

Aim 1. To assess the effectiveness of a micro-mobile foot compression device that provides mild compression to help reduce peripheral edema as compared to baseline in patients with both diabetes and lower extremity edema in a four-week observational clinical trial of 30 patients.

Hypothesis 1: The micro-mobile foot compression device will result in edema reduction when compared to baseline peripheral edema for the study population.

Aim 2. To assess the effect of micro-mobile foot compression device on the macro and micro lower extremity circulation as measured by Ankle Brachial Index (ABI) and Skin Perfusion Pressure (SPP) Measurements.

Hypothesis 2: The micro-mobile foot compression device will help improve macro and micro- circulation in the lower extremity of patients with diabetes and lower extremity edema as compared to baseline. We expect to see positive changes in ABI and SPP measurements.

Aim 3. To assess the effect micro-mobile foot compression device on the quality of life quantified using the validated, international quality of life assessment survey SF12, fear of falling quantified by FES-I, and risk of falling assessment quantified by gait, balance and spontaneous daily physical activity of patients with diabetes and lower extremity edema.

Hypothesis 3. The micro-mobile foot compression device will improve the quality of life, lower the risk of falling, lower fear of falling, and improve activity level of patients as compared to baseline assessments.

Section E: Protocol Risks/Subjects

E1. Risk Category

Category 2: Research involving greater than minimal risk, but presenting the prospect of direct benefit to the individual subjects.

E2. Subjects

Gender:

Both

Age:

Adult (18-64 yrs), Geriatric (65+ yrs)

Ethnicity:

All Ethnicities

Primary Language:

English, Spanish

Groups to be recruited will include:

Patients

Which if any of the following vulnerable populations will be recruited as subjects?

Vulnerable populations require special protections. How will you obtain informed consent, protect subject confidentiality, and prevent undue coercion?

E3. Pregnant woman/fetus

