Other assessments: Other relevant assessments are Demographic/Health questionnaire, the Mini-Metal State Exam, the mobility-tiredness scale, Barthel Index, Depression Scale, fear of falling (Short-Falls Efficacy Scale – International)[25], quality of life (SF-12 Health Survey)[26], Fried Frailty Criteria, Foot Questionnaire, Pain Assessment, Fall Log and Contact Agreement, Physical activity log, follow-up questionnaire, and Shoe-fit test

AVEX insole: The AVEX insole will be given to the subject. The research personnel will adjust the clutching reel (BOA technology) in order to ensure a comfortable shoe fit. The research personnel will also provide device education to the subject and will answer any questions which may arise.

Study Day 1, Visit 2 48-hour follow up: All participants will be asked to return to clinic approximately 48 hours after visit 1. In this visit, (1) any adverse events will be assessed; (2) activity measurement (body sensor) will be returned; (3) AVEX insole data will be downloaded to ensure operability and patient compliance; and (4) further device education will be provided in case any issues have risen

Study Day 2, Visit 3 1-week follow-up: All participants will be asked to return to clinic approximately 1 week after visit 1. In this visit, (1) any adverse events will be assessed; and (2) AVEX data download to ensure operability and patient compliance. Device education will be provided if needed. The subject will be asked to return the device at their next visit. Similar assessments performed during visit 1 may be performed again during this visit.

Study Day 3, Visit 4 4-week follow-up: All participants will be asked to return to clinic approximately 4 weeks after visit 1. In this visit, outcome assessment using similar assessments described for Study Day 0 will be performed. In addition, benefit and user-friendliness of the AVEX insoles and Boa Technology 'Clutch Reel' will be assessed using a questionnaire. The subject will return the device back to the research personnel.

Patients will be asked to wear a comfortable shirt which holds a small activity monitor (PAMSys) for a period of 48 Hours (2 days). Patients will be requested to return this device via a pre-paid FEDEX envelope

Study Day 4, Visit 5 Three month follow-up: All participants will be contacted by the study coordinator approximately three months post the last study visit (Visit 4) to document potential incident of diabetic foot ulcer or falls.

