The AVEX Footbeat insole is an investigational device, which has been designed to enhance blood flow to lower extremities via a Micro-Mobile Foot Compression Device. The compression component applied pressure under your foot arch. We will perform initial screening to ensure the safety of the device. But as any new insole, there is some risk that the insole caused some discomfort or cause development of foot ulcers. It is important to notify us if you feel discomfort on wearing the insoles or if you feel excessive pressure to your feet because of wearing the AVEX Footbeat insole.

The study device and technology is completely non-invasive, safe, non-toxic and non-ionizing. The potential risks to you are minimal. However, like any battery powered systems, there is a minimum risk of sensor malfunctioning. In addition, the study devices are not waterproof, and although they use a low powered battery (similar to a cell-phone battery), in order to avoid any risk of shock the monitor should not be submerged or saturated with fluids during operations or cleaning.

You must be willing to charge device battery daily. Otherwise they will not receive benefit from compression component during treatment.

The assessments described above are expected to be minimal risk and probability and magnitude of harm or discomfort anticipated in the research are not greater in and of themselves than those ordinarily encountered in daily life or during the performance of routine physical or psychological examinations or tests.

Please note that there is also the possibility for loss of confidentiality. The PI and the research team will minimize the possibility of for loss of confidentiality by keeping all the physical data locked in cabinets only accessible to the research team. The electronic data will be kept on network password protected institutional computers. And, subject PHI will be coded as much as possible to minimize the potential for loss of confidentiality.

H2. Data and safety monitoring plan

Do the study activities impart greater than minimal risk to subjects?

No

H3. Coordination of information among sites for multi-site research

Is the BCM Principal Investigator acting as the SPONSOR-INVESTIGATOR for this multi-site research?

No or Not Applicable

Is BCM the COORDINATING CENTER for this multi-site research?

No or Not Applicable

Section I: Potential Benefits

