Describe potential benefit(s) to be gained by the individual subject as a result of participating in the planned work.

There may be no direct benefit to you by being in this study. However, the device may improve blood flow and reduce the number of traumatic amputations.

Describe potential benefit(s) to society of the planned work.

What the researchers find out from this study may help other people with diabetes and history of foot ulcers. This research utilizes a new device to improve blood flow, which may help to prevent diabetic foot ulcer and enhance balance; it is part of a larger prevention initiative to reduce the high number of traumatic amputations associated with the diabetic foot disease.

Do anticipated benefits outweigh potential risks? Discuss the risk-to-benefit ratio.

The risks involved with this study are very minimal. There is a possibility for a loss of confidentiality and some risks still remain unknown. There is also the possibility of minimal risks associated with use of the devices in this study. However, there is a chance that the device may provide some benefits. Therefore, the anticipated benefits outweigh the potential risks.

Section J: Consent Procedures

J1. Waiver of Consent

Will any portion of this research require a waiver of consent and authorization?

Yes

Please describe the portion of the research for which a waiver is required. (Example: chart review to determine subject eligibility)

We will review our patient charts to determine and verify patient eligibility.

Explain why the research and the use or disclosure of protected health information involves no more than minimal risk (including privacy risks) to the individuals.

A plan exists such that only the PI and clinical database administrator have access to these password-protected identifiers,

which are subsequently removed when sharing data with co-investigators, analyzing data, and reporting or disseminating aggregate outcome data (often reported as rates) in scholarly publications and scientific presentations. The use or disclosure of PHI involves no more than minimal risk to the individuals and the waiver will not adversely affect the privacy rights and the welfare of the individuals.

The PHI will not be reused or disclosed to (shared with) any other person or entity, except as required by law, for authorized oversight of the research study, or for other research for which the use or disclosure of the PHI would be permitted under the Privacy Rule.

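### Section E1 rates the study above minimal risk, but H2 answers No to the same question and gives no monitoring plan, and adverse events are not a named item at Visit 4

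*Combined protocol and SAP*

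**What the plan says.** All places are in the combined protocol and SAP.

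- **E1 (Risk Category):** "Category 2: Research involving greater than minimal risk, but presenting the prospect of direct benefit to the individual subjects".
- **H2 (Data and safety monitoring plan):** the form asks "Do the study activities impart greater than minimal risk to subjects". The answer is No, and the text goes straight on to H3.
- **H1 (Potential Risks/Discomforts):** "The AVEX Footbeat insole is an investigational device", and "there is some risk that the insole caused some discomfort or cause development of foot ulcers". The same section also says "The potential risks to you are minimal", and asks participants to tell the team about discomfort or excessive pressure.
- **Section I (Potential Benefits):** "The risks involved with this study are very minimal", although it also concedes that "some risks still remain unknown".
- **F1 (Design):** one inclusion criterion is being at risk of a diabetic foot ulcer.
- **F2 (Procedure):** adverse-event assessment is a numbered item at Visit 2 (48 hours) and Visit 3 (1 week). At Visit 4 (4 weeks) the text says that "outcome assessment using similar assessments described for Study Day 0 will be performed", and adds a user-friendliness questionnaire and return of the device. Adverse events are not named there. Visit 5 is a contact about three months after Visit 4 to record ulcers and falls.

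**The concern.** The risk level is the question that H2 puts under its monitoring-plan heading, and the protocol answers it in two opposite ways. A reader cannot tell which level governs the study. H2 is also the only section headed as a monitoring plan, so if its answer is followed the document contains no such plan.

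The protocol gives its own reasons why this matters. The harm named in H1 is the one the enrolled patients are already prone to. The background says clinicians hesitate to use compression where arterial disease may be present. The stated purpose includes not harming the arterial supply, and only an ABI below 0.5 is excluded, so patients with milder arterial disease can enter. H1 asks participants to report discomfort, but F2 tests the same participants for loss of foot sensation, and those who have it may not feel a problem.

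The Visit 4 list adds a practical gap. Visit 4 closes the period on the device, and it is the one clinic visit after baseline at which adverse events are not a named item.

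**Working it through.** The plan states no figure on this point, and the check needs no rate, effect size or sample size. It is a comparison of text.

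**Step 1. Risk level, section by section.**

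| Section | What it implies |
|---|---|
| E1 | Above minimal risk |
| H1, device wording | Minimal |
| H1, ulcer sentence | The device may cause a foot ulcer |
| H2 | Not above minimal risk |
| Section I | Very minimal, with some risks unknown |

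E1 and H2 address the same attribute of the same study and give opposite answers. H1 is mixed: its general wording agrees with H2, while its ulcer sentence sits more easily with E1. Section I agrees with H2 in its summary but admits unknown risks. All of this is current text, not an amendment history.

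**Step 2. Is a plan given elsewhere?** The public text names nobody to review adverse events, sets no frequency of review and describes no reporting path. The analysis plan in G2 does not mention adverse events or ulcers. It uses ABI and SPP only as outcomes or predictors. Absence is judged on the public text, but H2, where a plan would sit, runs unbroken into H3.

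**Step 3. Where are adverse events named?**

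| Visit | Named adverse-event assessment | Other safety-relevant content |
|---|---|---|
| 2 (48 hours) | Yes | Device data download |
| 3 (1 week) | Yes | Baseline-type assessments optional |
| 4 (4 weeks) | No | Assessments similar to Day 0, device returned |
| 5 (about 3 months after Visit 4) | No | Ulcers and falls only |

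Adverse events are therefore named at two of the three clinic visits after baseline, and the exception is the end of exposure.

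**Step 4. What would Visit 4 still pick up?** The Day 0 assessments include a skin, vascular and neurological examination, ABI, SPP, a pain assessment, a foot questionnaire and a fall log. F2 also provides for photographs, video and thermal images to watch for worsening. An ulcer or a loss of perfusion present at week 4 should be met by these.

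**Step 5. What is left?** The remainder is any adverse event after Visit 3 that those sources do not show. Examples are an event that has resolved by Visit 4, or one of a kind that no listed assessment looks for.

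**The case against.** The strongest reply is that H2 is a form answer consistent with the risk wording in H1 and Section I, that E1 is the outlier, and that safety is watched in practice. Adverse events are assessed at 48 hours and 1 week, Visit 4 repeats assessments like those of Day 0, images are taken to detect worsening, ulcers and falls are sought about three months later, and participants are told to report discomfort. Recruitment is from the investigator's own practice.

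Much of this stands, and it rules out three stronger readings that a reader might infer.

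- *That nobody reviews safety.* The text supports only that the reviewer, frequency and reporting path are not specified.
- *That events between week 1 and week 4 have no point of capture.* The Visit 4 assessments and the later contact cover the two harms of most concern, ulcers and loss of perfusion. The three weeks between Visits 3 and 4 are an interval between visits, not a period in which nothing is recorded.
- *That the No in H2 is why no plan was written.* This is plausible from the layout of the form, but the documents do not say so.

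The reply does not remove the contradiction. Agreement between H2 and some of H1 and Section I leaves E1 saying the opposite, and H1's own ulcer sentence pulls the other way. Nor does it put adverse events on the Visit 4 list: an instruction to perform similar assessments is loose, and Day 0 has no adverse-event item to repeat.

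**Conclusion.** The point holds in two parts.

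1. **E1 against H2: wrong as written.** The study is both above and not above minimal risk, and the monitoring-plan section contains no plan. This rests on the text alone and needs no assumption. Which category is right is for the investigator and the review board to decide.
2. **Visit 4: a narrower gap.** Adverse events are not named at the end of device exposure, so some events after week 1 could go unrecorded. This assumes that the visit lists are followed as written. It does not extend to ulcers or perfusion loss still present at week 4, which the repeated assessments should find.

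The size cannot be put as a number, because the plan gives no adverse-event rate and no result depends on one. The point deserves correction before the study runs because it concerns the protection of participants and costs very little to put right.

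**What to change.** - **Reconcile E1, H1, H2 and Section I to one risk level.** If E1 stands, change the H2 answer to Yes, bring the minimal-risk wording in H1 and Section I into line, and complete a short plan. The plan should say who reviews adverse events, how often and by what route they are reported, and that ulcers and the ABI and SPP results already collected are part of the review. If instead H2 stands, change E1 and explain how the ulcer sentence in H1 fits the lower level.
- **Whichever level is chosen,** add a named adverse-event assessment to the Visit 4 list, covering the period since Visit 3.
- Any clinical thresholds for action are left to the investigator.

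The cost, if E1 stands, is one form answer, a short plan with matching wording, and one line at a visit already scheduled. No new visit, measurement or participant is needed.
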